10. ANALYSIS OF SAFETY DATA

Summaries of safety results will be presented by treatment group. All clinical safety variables will be analyzed using the SAF.

For safety variables (i.e., adverse events, laboratory measurements, vital signs, physical examination, and electrocardiography parameters), 3 observation periods are defined:

- The pre-treatment period is defined as the time from signing the ICF to prior to the first dose of study drug
- The on-treatment period is defined as the time from Day 1 (on or after administration of the first dose of study drug) to the date of last dose of study drug + 14 days
- The follow-up period is defined as the time from the end of the on-treatment period (i.e., date of last dose of study drug + 15 days) plus 12 weeks (i.e., 84 days)

Additionally, the treatment-emergent period is defined to comprise of the on-treatment and follow-up periods.

To support the assessment of the secondary endpoint of the incidence of treatment-emergent adverse events (TEAEs) from baseline through the end of treatment (week 24-52), summary tables will be provided for AEs that occur during the on-treatment period. A separate set of summary tables will be provided for AEs that occur during the on-treatment or follow-up safety periods (i.e, during the treatment-emergent period).

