#### 9.1.1. Footnotes for the Schedule of Events Table

#### Footnotes for Table 1 Schedule of Events

\*Visits 5, 7, 9, and 10 will be performed as phone visits for patients not receiving OCS at baseline. For patients receiving OCS at baseline, these visits should be performed in-clinic if the patient remains on OCS on the day of the clinic visit. If OCS has been discontinued, these visits can be either in-clinic or performed as a phone visit at the discretion of the investigator. Assessments/procedures marked with an asterisk should only be performed if the visit occurs in-clinic.

\*\*After the last patient has completed visit 14/week 24 of the treatment period or withdrawn from the study, all patients still currently in the treatment period (between visit 15/week 26 and visit 27/week 50) should return to the clinic 2 weeks from their last dose/treatment administration to complete their EOT visit and all its applicable assessments. For patients who have withdrawn from the study treatment but remain in the study, the EOT visit will take place 2 weeks from their last visit. All patients must have their EOS visit 12 weeks after their EOT visit.

- a. Prior to screening, patients must be on a stable background therapy for asthma which may include ICS in combination with a second controller medication (eg, LABA, LTRA, theophylline, etc) for at least 3 months with a stable dose ≥1 month prior to baseline. Patients requiring a third controller are allowed to participate in this study. The third controller should also be used for at least 3 months with a stable dose ≥1 month prior to visit 1. Patients requiring systemic steroids of up to 10 mg per day (or up to 30 mg every alternate day) as controller medication are permitted.
- b. Randomization/baseline visit is defined as day 1. The visit schedule should be adhered to within  $\pm 1$  week for the screening period,  $\pm 3$  days for the randomized IMP treatment period, and  $\pm 7$  days for the post-IMP treatment period.
- c. All assessments at visit 2 (day 1) are to be conducted pre-IMP dose except for the assessment of local tolerability of SC injections.

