## 11.4.5.1. Adverse Events

## **Definitions**

For safety variables, 3 observation periods are defined:

- The pre-treatment period is defined as the time from signing the ICF to prior to the first dose of study drug.
- The on-treatment period is defined as the time from day 1 (on or after administration of the first dose of study drug) to the date of last dose of study drug +14 days or the date of patient last contact, whichever is earlier
- The follow-up period is defined as the time from the date of last dose of study drug +15 days to the EOS visit or the date of patient last contact, whichever is earlier

The treatment-emergent period is comprised of the on-treatment and follow-up periods.

Treatment-emergent adverse events are defined as those that are not present at baseline or represent the exacerbation of a pre-existing condition during the treatment-emergent period.

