#### Analysis

All AEs reported in this study will be coded using the Medical Dictionary for Regulatory Activities (MedDRA®).

Summaries of all TEAEs by treatment group will include:

- The number (n) and percentage (%) of patients with at least 1 TEAE by SOC and PT
- TEAEs by severity (according to the grading scale outlined in Section 10.2.4), presented by SOC and PT
- TEAEs related to treatment presented by SOC and PT
- Treatment-emergent AESIs (defined with a PT or a prespecified grouping)

Deaths and other SAEs will be listed and summarized by treatment group.

Treatment-emergent adverse events leading to permanent treatment discontinuation will be listed and summarized by treatment group.

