10.1. Adverse Events

All new or worsening AEs occurring from the time of signing of the ICF through the end of the study will be recorded and coded using the MedDRA® dictionary. The definitions of AEs, serious adverse events (SAEs), and adverse events of special interest (AESIs) are provided in Sections 10.2.1-10.2.3 of the protocol.

Pre-treatment AEs and TEAEs are defined as follows:

- Pre-treatment AEs are AEs that developed or worsened in severity during the pre-treatment period, as defined above.
- TEAEs are AEs that developed or worsened in severity compared to baseline during the on-treatment and follow-up periods, as defined above. As only new AEs that were not present at baseline and pre-existing AEs that worsen during the on-treatment and follow-up periods will be summarized in this study, all AEs collected during the on-treatment and follow-up periods are considered TEAEs.

Adverse events will be summarized with incidence tables. Adverse event incidence tables will present the number and percentage of patients experiencing an AE within each treatment group, sorted by decreasing frequency of SOC and PT in the dupilumab treatment group. Multiple occurrences of the same event in a patient will only be counted once in the summaries. For tables showing AE severity, if a patient has multiple occurrences of the same PT or SOC, only the worst severity will be counted in the summary.

AE summaries will be presented for the TEAEs. The following summaries for TEAEs will be presented by treatment group:

- Overview of TEAEs, consisting of the number and percentage of participants with any TEAE, with any drug-related TEAE, with any TEAE leading to permanent discontinuation of study drug, with any TEAE resulting in death, with any treatment-emergent SAE, with any treatment-emergent, drug-related SAE, and with any treatment-emergent SAE leading to permanent discontinuation of study drug.
- TEAEs by primary SOC and PT
- TEAEs by primary SOC, high level term (HLT), and PT
- TEAEs by primary SOC, PT, and severity (according to the grading scale in Section 10.2.4 of the protocol)
- TEAEs by primary SOC and PT that occur in $\geq 5\%$ of patients in either treatment group
- TEAEs related to study drug by primary SOC and PT
- Injection site reaction TEAEs by primary SOC, HLT, and PT
- TEAEs with fatal outcome by primary SOC and PT
- Serious TEAEs by primary SOC and PT
- TEAEs leading to permanent discontinuation of study treatment by primary SOC and PT

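### Deaths, SAEs and AESIs that start more than 99 days after the last dose fall outside the SAP's adverse-event tables, which matters for patients who stop drug early but stay in the study

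*SAP*

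**What the plan says.** **Window.** SAP Section 10 runs the on-treatment period "to the date of last dose of study drug + 14 days" and the follow-up period from "date of last dose of study drug + 15 days) plus 12 weeks (i.e., 84 days". It adds that "the treatment-emergent period is defined to comprise of the on-treatment and follow-up periods".

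**Tables.** SAP 10.1 states that "AE summaries will be presented for the TEAEs". The fatal-outcome and serious-event tables in that list are TEAE tables, and the AESI summaries in SAP 10.1.1 are likewise limited to treatment-emergent events.

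**Collection.** SAP 10.1 also states that "All new or worsening AEs occurring from the time of signing of the ICF through the end of the study will be recorded".

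**Protocol.** Section 11.4.5.1 has no day cap: "The follow-up period is defined as the time from the date of last dose of study drug +15 days to the EOS visit", or to last contact if that is earlier. After its list of TEAE summaries it says separately: "Deaths and other SAEs will be listed and summarized by treatment group".

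**Who stays.** Protocol 8.4.2 encourages patients who permanently stop study drug to stay in the study and attend the remaining visits, and SAP 5.2 allows for such patients. Protocol 9.1.1 adds: "All patients must have their EOS visit 12 weeks after their EOT visit".

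**Disclosure.** SAP 1.4 records that the follow-up definition was changed to give every patient a consistent reporting window. It does not say what happens to deaths or SAEs after that window.

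**The concern.** An event that starts after the window closes is neither pre-treatment nor treatment-emergent under the SAP's definitions, so none of the planned AE tables has a place for it. The protocol's commitment to summarise deaths and other SAEs by arm has no counterpart in the SAP that covers the whole of follow-up.

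The patients exposed to this gap are ones the design wants to keep. Their FEV1 after stopping drug enters the primary analysis through Week 24 (SAP 7.2.1), and their off-drug severe exacerbations count through EOT (SAP 7.2.2). SAP 9.3 and 9.4 summarise concomitant medications and procedures up to EOT and then to last contact. For an early stopper with a late EOT, a procedure could therefore be tabulated while the SAE that led to it is not.

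With about 30 patients per arm, one late death or SAE is 1/30, about 3% of an arm.

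**Working it through.** **Inputs.** On-treatment period ends at last dose + 14; follow-up is 12 weeks from last dose + 15 (SAP 10). Week w is Day 7w + 1, as in SAP 11.4, Table 3 (Week 12 = Day 85). For patients on drug, EOT is 2 weeks after the last dose; EOS is 12 weeks after EOT (Protocol 9.1.1). Visit tolerances are ±3 days for EOT and ±7 for EOS (Protocol Table 1).

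**1. The SAP's own figure.** 12 × 7 = 84 days, as stated. Window closes at 15 + 84 = last dose + 99. If the 84 days run from the end of the on-treatment period, it closes at 14 + 84 = last dose + 98.

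**2. Patients who complete treatment.** Nominal EOS = 14 + 84 = last dose + 98, inside the window on either reading. The latest EOS within tolerance is (14 + 3) + (84 + 7) = last dose + 108, so at most 108 − 99 = 9 days are uncovered (10 on the other reading).

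**3. Patients who stop drug but stay to EOS.** Uncovered days = EOS day − (last-dose day + 99). EOS is Day 169 + 84 = 253 for EOT at Week 24, and Day 365 + 84 = 449 for EOT at Week 52. Percentages are of the time from Day 1 to EOS (252 or 448 days).

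| Last dose | Window closes | EOT Week 24 | EOT Week 52 |
|---|---|---|---|
| Week 4 (Day 29) | Day 128 | 125 days (50%) | 321 days (72%) |
| Week 8 (Day 57) | Day 156 | 97 days (38%) | 293 days (65%) |
| Week 12 (Day 85) | Day 184 | 69 days (27%) | 265 days (59%) |
| Week 20 (Day 141) | Day 240 | 13 days (5%) | 209 days (47%) |

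On the 98-day reading each gap is one day longer. Under the protocol's definition, which runs to EOS or last contact, every gap is zero.

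**4. The missed-dose rule.** Protocol 8.4.2.2 takes a patient out of the study after more than 4 consecutive missed doses. With dosing every 14 days, the fifth missed dose falls at 5 × 14 = last dose + 70, and the next two-weekly visit at + 84. Both lie inside the window. If this rule governs permanent stoppers, the gaps in step 3 do not arise. If Protocol 8.4.2 and SAP 5.2 govern, they do.

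**The case against.** **The cut-off is deliberate and defensible.** SAP 1.4 discloses it. Protocol 3.2.1 chose 12 weeks as the time for drug levels to fall below quantification, and the SAP window runs at least that long after the last dose. Not calling an event months later treatment-emergent is a reasonable exposure-based choice, and a TEAE window running to EOS would give early stoppers longer observation than completers. This stands as a defence of the TEAE tables. It does not explain why no table covers the remaining deaths and SAEs, which the protocol says will be summarised.

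**The gap may be empty.** The missed-dose rule could remove the patients concerned, and the documents do not say how many stop early and stay. This stands as a limit on size. The rule sits under temporary discontinuation and pulls against Protocol 8.4.2 and SAP 5.2; those passages must be reconciled.

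**The events are not lost.** A reader might infer that late events are reported nowhere. The documents do not support that. Protocol 10.1.2 requires narratives for SAEs and AESIs, and Protocol 10.4 commits the sponsor to reporting all safety observations in the CSR. SAP 1.4 keeps the listings that the CSR requires. A death could show as a reason for discontinuation in the disposition tables, severe exacerbations count through EOT, and the laboratory PCSV analysis uses all measurements. None of these is the by-arm summary that the protocol promises.

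**Completers.** A reader might also infer that the window misses the scheduled EOS visit. Step 2 shows that it does not; the shortfall is a minor effect of visit tolerances.

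**Conclusion.** The point holds in a limited form. The SAP's AE, death, SAE and AESI tables omit events that start more than 99 days after the last dose (98 on the other reading), and the SAP plans no table to meet the protocol's commitment on deaths and other SAEs for that later period. Events in the same patients before the cut-off are tabulated.

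In the cases worked above, the gap for an early stopper who remains to EOS runs from 13 days (last dose Week 20, EOT Week 24) to 321 days (last dose Week 4, EOT Week 52). These figures assume that the patient stays to EOS and is not removed under Protocol 8.4.2.2. The longest ones also need a Week 52 EOT.

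A reader might infer that the omission is unbalanced between arms or concentrated in patients who stopped for tolerability. Nothing in the documents shows either. The primary endpoint is unaffected, as are the on-treatment AE tables that support the secondary safety endpoint.

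**What to change.** Leave the fixed-window TEAE tables as they are. Add one table by treatment group of all deaths, SAEs and AESIs from first dose through EOS or last contact, regardless of time since last dose, with patient-years of observation for each arm. State in SAP 1.4 that the TEAE tables exclude later events and that this table covers them. Widening the TEAE window by the visit tolerances would not help, because it would leave nearly all of the early-stopper gap open.

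Separately, reconcile Protocol 8.4.2.2 with Protocol 8.4.2 and SAP 5.2, so that it is clear which patients are followed after stopping drug.

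The cost is one extra table and a few lines of SAP text. The drawback is unequal observation time between patients, which is why the patient-years should be shown.

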#### 4.1.2. Secondary Endpoints

The secondary endpoints are:

- Annualized rate of severe respiratory exacerbations, defined as new onset of symptoms or clinical worsening of respiratory symptoms requiring systemic corticosteroid treatment for ≥3 consecutive days; for patients who are on maintenance systemic corticosteroids, at least double the dose of maintenance systemic corticosteroids for ≥3 consecutive days (with or without antibiotic therapy if indicated) over the 24- to 52-week treatment period
- 2. Annualized rate of ABPA-related exacerbations, defined as severe respiratory exacerbations (as defined above) that are associated with a doubling of serum total IgE from the prior pre-exacerbation value, over the 24- to 52-week treatment period
- 3. Annualized rate of severe respiratory exacerbations requiring either hospitalization or observation for >24 hours in an ED/urgent care facility during the 24- to 52-week treatment period
- 4. Change from baseline in ACQ-5 over the 24- to 52-week treatment period
- 5. Change from baseline in SGRQ total score over the 24- to 52-week treatment period
- 6. Percentage of participants achieving a reduction in the SGRQ score of 4 points or greater from baseline to weeks 12, 24, 36, and 52
- 7. Percent change from baseline in total IgE in serum over the 24- to 52-week treatment period
- 8. Percent change from baseline in *A fumigatus*-specific IgE in serum over the 24- to 52week treatment period
- 9. Percent and absolute change from baseline in FeNO over the 24- to 52-week treatment period
- 10. Incidence of treatment-emergent adverse events (TEAEs) from baseline through the end of treatment (week 24 to 52)
- 11. Immunogenicity of dupilumab, as determined by the incidence, titer, and clinical impact of treatment-emergent ADA to dupilumab over time
- 12. Concentrations of functional dupilumab in serum by treatment regimen at each assessment time point from baseline to the end of study

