# 6. STUDY DESIGN

### 6.1. Study Description and Duration

This phase 2, global, multicenter, randomized, double-blind, placebo-controlled study of dupilumab is designed to evaluate the efficacy and safety of dupilumab in patients with ABPA. Approximately 60 patients will be enrolled in the study. The study consists of 3 study periods:

- Screening period (4 weeks)
- Randomized treatment period (24- to 52 weeks)
- Post-treatment follow-up period (12 weeks)

This study employs a variable treatment duration from 24- to 52 weeks. Patients enrolled in the trial will remain in the treatment period for up to a maximum of 52 weeks or until the last patient completes a minimum treatment period of 24 weeks. Of note, the accrual and drop-out rates will be closely monitored. The maximum treatment duration of 52 weeks will not be changed. For further explanation regarding the duration of the randomized treatment period, refer to Section 9.1.1.

Patients who meet the eligibility criteria will be randomized (1:1) to 1 of the following treatment groups:

- Dupilumab 300 mg, after a loading dose of 600 mg on day 1, administered SC Q2W
- Matching placebo, administered SC Q2W

Randomization will be stratified by region (pooled country), chronic systemic corticosteroid use (yes/no) at screening, and by oral antifungal use (yes/no) at screening.

Rescue courses of systemic steroids for exacerbations, as determined by the investigators, will be permitted during the study. Patients will be required to continue all background asthma controller medications (ICS) with or without long-acting beta agonist (LABA), leukotriene receptor antagonist (LTRA), or long-acting muscarinic receptor antagonist (LAMA) without any changes in the dose or regimen during the study period. However, if 2 or more exacerbations occur during the treatment period, changes to background therapy (eg, changes to background asthma controller medication or initiation of antifungal therapy) may be made at the investigator's discretion.

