9. SUMMARY OF EXPOSURE DATA

9.1. Study Drug Exposure and Compliance

Study drug exposure and compliance will be summarized by treatment group for the SAF population.

The duration of exposure to study treatment (in days) during the study will be presented by treatment group and calculated for each individual patient as:

(Date of last study drug administration – date of first study drug administration) + 14 days

The calculation does not take into account temporary dosing interruptions (including dosing interruptions due to COVID-19).

The number and percentage of patients randomized and exposed to double-blind study drug will be presented by the following, cumulative, duration of exposure categories: ≥ 14 days, ≥ 28 days, ≥ 42 days, etc., with a 14-day increment added for each subsequent category. The highest category displayed will account for the maximum duration of exposure observed in the study.

In addition, duration of exposure to study treatment during the study will be summarized for each treatment group by the following summary statistics: arithmetic mean, sample SD, minimum, Q1, median, Q3, and maximum.

Compliance with the study drug will be calculated as follows:

(Number of study drug injections during the exposure period)/(Number of planned study drug injections during the exposure period) $\times 100\%$

The number of study drug doses administered and treatment compliance will be summarized for each treatment group by the following summary statistics: arithmetic mean, sample SD, minimum, Q1, median, Q3, and maximum. Treatment compliance will also be presented by the following ranges: $<80\%$ and $\geq 80\%$.

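### TEAE incidence (secondary endpoint 10) is planned only as crude percentages over on-treatment windows that vary from about 24 to 52 weeks, so it has no common time horizon; supplementary exposure-adjusted rates or a week-24 incidence would supply one

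*SAP*

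**What the plan says.** Protocol 4.1.2 words secondary endpoint 10 as "Incidence of treatment-emergent adverse events (TEAEs) from baseline through the end of treatment (week 24 to 52"). Protocol 6.1 sets the length of treatment: "This study employs a variable treatment duration from 24- to 52 weeks". A patient stays on treatment until week 52 or until the last one enrolled has reached week 24, whichever comes first, so one study-wide date ends treatment for everyone who has not yet reached week 52.

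SAP 10 defines the on-treatment period as running from Day 1 "to the date of last dose of study drug + 14 days". For endpoint 10, "summary tables will be provided for AEs that occur during the on-treatment period"; a second set of tables adds the follow-up period. SAP 10.1 fixes the measure: "Adverse event incidence tables will present the number and percentage of patients experiencing an AE within each treatment group", with each patient counted once per event. Protocol 11.4.5.1 uses the same measure: "The number (n) and percentage (%) of patients with at least 1 TEAE by SOC and PT".

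Neither document plans a patient-year rate, a time-to-first-event summary or a fixed-horizon table for adverse events, and nothing is blacked out in the adverse event sections. Exposure is handled separately: under SAP 9.1, "duration of exposure to study treatment during the study will be summarized for each treatment group", and SAP 9.2 does the same for duration of observation.

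**The concern.** A proportion of patients with an event is easy to read when everyone is followed for the same time. Here one patient may contribute 24 weeks at risk and another 52, and both count equally in the denominator. The reported figure then depends on the accrual pattern and the date the last patient reached week 24 as well as on the drug.

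Early stopping adds a second source of unequal time. Protocol 8.4.2 encourages patients who stop drug to stay in the study, but the on-treatment window closes 14 days after their last dose. If stopping differs between arms, so does the time in which an event can count. At stake is how the safety endpoint is read: the absolute incidence has no stated horizon, and a difference between arms could partly reflect time at risk.

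**Working it through.** The documents state no figure for TEAE incidence, so there is none to reproduce. The stated 96% power concerns week-24 FEV1 and has no bearing here.

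**Inputs from the documents.** Treatment of 24 to 52 weeks and 1:1 randomisation (Protocol 6.1); about 30 patients per arm (Protocol 7.1); on-treatment window to last dose plus 14 days (SAP 10).

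**Assumptions.** Constant hazard; planned durations uniform on 24 to 52 weeks unless stated; event rates as shown. The documents give no adverse event rate, duration mix or discontinuation by arm.

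**1. Absolute incidence.** Risk by week *w* is 1 − exp(−*r* × *w*/52), with *r* first events per year. The average over uniform durations is 1 − [exp(−24*r*/52) − exp(−*r*)] / (28*r*/52).

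- *r* = 1: 24 weeks, 1 − exp(−0.462) = 37%; 52 weeks, 1 − exp(−1) = 63%. Uniform mix: 1 − (0.630 − 0.368)/0.538 = 51%. Half at 52 weeks and half uniform: (63.2% + 51.3%)/2 = 57%.
- *r* = 0.5: 21%, 39%, 30% and 35% respectively.

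For an uncommon event with a 52-week risk of 10%, the 24-week risk is 4.7%. The rate is about 10.6 per 100 patient-years at either duration.

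**2. Chance imbalance between arms.** The SD of a uniform 24-to-52-week duration is 28/√12 = 8.1 weeks. The standard error of the difference in mean duration is 8.1 × √(2/30) = 2.1 weeks, so the 95% range is ±1.96 × 2.09 = ±4.1 weeks. In 40,000 simulated trials of 30 versus 30 with equal hazards:

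| Assumed 52-week risk | Mean crude difference | SD from exposure imbalance | Total SD |
|---|---|---|---|
| 10% | 0.000 | 0.4 points | 6.8 points |
| 30% | 0.000 | 1.1 points | 10.9 points |
| 80% | 0.000 | 2.0 points | 12.1 points |

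**3. Differential early stopping.** Assume 5% stop early in one arm and 20% in the other, at times uniform over weeks 0 to 24, with equal hazards. Crude risk in an arm = (1 − *d*) × full-course average + *d* × early-stopper average, where *d* is the proportion stopping early. For a 52-week risk of 30% the two averages are 22.8% and 7.8%. The arms then show 0.95 × 22.8 + 0.05 × 7.8 = 22.1% and 0.80 × 22.8 + 0.20 × 7.8 = 19.8%, a ratio of 1.11. For 52-week risks of 10% and 80% the ratios are 1.12 and 1.10. The true rate ratio is 1.00 throughout.

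**The case against.** The strongest reply is that the SAP reports the endpoint as the protocol words it, that safety is descriptive, and that this is a reporting preference. Much of that stands, and it rules out several stronger readings.

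- A reader might infer that the endpoint covers no defined period. It does: each patient's window is defined. What is missing is a common length.
- A reader might infer that exposure imbalance is ignored. SAP 9.1 and 9.2 tabulate exposure and observation time by arm, so an imbalance would be visible. It is just not used in the adverse event tables.
- A reader might infer that variable duration biases the arm comparison. The planned cut-off does not depend on arm and gives no expected bias.
- A reader might infer that the plan was adapted to variable duration for exacerbations (the log-time offset in SAP 7.2.2) but not for adverse events. The amendment history shows exacerbations were already an annualised rate under the fixed 52-week design, so the offset is not evidence of an oversight.
- A reader might say the endpoint understates the 52-week risk. Endpoint 10 is not defined as a 52-week risk. The Amendment 3 rationale also notes that some patients would already have had 52 weeks of treatment, and the more who did, the closer the crude figure lies to 63% in the example above.

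It can also be said that a reader could divide patients with an event by N times mean exposure. For uncommon events that works: at 10.6 per 100 patient-years and 38 weeks (0.728 years), the risk is 1 − exp(−0.0772) = 7.4%, and 0.0743/0.728 gives 10.2 per 100. For common events it fails. At 161.5 per 100 patient-years the risk is 1 − exp(−1.176) = 69%, and 0.6915/0.728 gives about 95 per 100, because time after the first event stays in the denominator. The planned exposure tables do not give time at risk to first event.

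**Conclusion.** The point holds as a gap in reporting. The planned TEAE percentage averages risk over follow-up of about 24 to 52 weeks, less for early stoppers, and nothing planned puts it on a common time basis. Under a constant hazard the span from shortest to longest full course is wide: 37% to 63% at 1 first event per year, and roughly a doubling for uncommon events.

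Between arms the effect is small. Chance imbalance adds little noise, and bias arises only if time on drug differs by arm for other reasons, chiefly early discontinuation. The 5% versus 20% case is an illustration; the documents give no arm-specific figures. All sizes rest on assumed rates, a constant hazard and an assumed duration mix. Efficacy conclusions are untouched. This is a cheap improvement, not a flaw in the safety analysis.

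**What to change.** In SAP 10.1 and 10.1.1, for any TEAE, serious TEAEs, TEAEs leading to permanent discontinuation and each AESI category, add one of the following by treatment group beside the planned percentages:

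- patients with at least one event per 100 patient-years at risk, counting time to the first event or to the end of the on-treatment period; or
- the incidence through week 24.

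Present either descriptively, without between-arm tests or intervals. The amendment history removed placebo comparisons from the secondary endpoints as underpowered, and with about 30 per arm such intervals for AESIs would say little.

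The patient-year rate accounts for unequal time on drug but assumes a roughly constant hazard, which suits early-clustered events poorly. The week-24 incidence avoids that assumption but does not by itself adjust for drug stopped before week 24. Either one supplements the percentages and replaces nothing.

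The cost is a few lines of SAP text and extra table columns. The inputs, adverse event start dates (SAP 11.2) and first and last dose dates (SAP 11.3), are already derived.
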